All subjects enrolled in the study will have thyroid function tests (TFT) which include serum TSH, total triiodothyronine (T3), total thyroxine (T4) and free T4 (fT4) assessed at baseline, at one month and two months following administration of ISOVUE. If TSH values are abnormal at either the one month or two month time points, further follow-up will be required at 6 and 12 months after the administration of ISOVUE to monitor subject's response and treatment (if any). Follow-up at 6 and 12 month post-dose time points will be performed using a pre-defined questionnaire.

The study will be conducted at approximately 10-20 sites in the United States.

Discussion of Study Design

The proposed study is designed as an intra-subject comparison of TSH, T3, and T4 values before and after administration of ISOVUE and will enroll pediatric subjects 0 to 3 years of age, who require a radiologic procedure with intravascular administration of ISOVUE as part of their standard of care.

The primary endpoint of this study is to evaluate the proportion of subjects exhibiting abnormal values of TSH following intravascular administration of ISOVUE. Thyroid function test data will be collected prospectively. Serum thyroid function testing at baseline, one month and two month post-dose time points will be performed at a local laboratory.

Abnormal TSH findings for subjects enrolled in the study will be compared to a reference population. As recommended by the FDA, the reference population for the study is represented by 3,214 infants who received potassium iodide prophylaxis on the second day of life at the time of the Chernobyl nuclear accident; 12 of the 3,214 infants ($p=0.003734$, 95% CI 0.002025, 0.006339) showed a transient increase of serum TSH levels and a decrease of fT4 levels after administration of potassium iodide.¹

As per FDA recommendation, sample size estimation for the current study has utilized the threshold incidence rate ($p=0.003734$) as the clinically meaningful value to rule out a safety concern about the proportion of children with abnormal TSH after exposure to ISOVUE.

Following FDA recommendations to be complied with:

- abnormal TSH in the study is defined as any TSH value above the normal age/gender-specific reference range provided by the respective local laboratories.
- hypothyroidism is defined as a TSH > 10 mIU/L (independent of fT4) or as a TSH above the normal age-specific reference range and an fT4 below the lower limit of the normal range.

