
Risk-Benefit Considerations

This study will enroll subjects who require a radiologic procedure with intravascular administration of ISOVUE as part of their standard of care; therefore, inclusion in the present clinical trial will not add any risk to the subject. Three blood draws of approximately 2.0 ml each will be performed in all subjects as part of the study, to assess serum TFTs before and after administration of ISOVUE.

Although subjects enrolled in the study will not directly benefit from this clinical trial, study results may be beneficial for pediatric subjects 0 to 3 years of age who will be exposed to iodinated contrast agents.

Study Duration

All subjects enrolled in the study will undergo the radiologic examination with administration of ISOVUE, as part of their standard of care; TFTs will be assessed at baseline, one month and two months post-dose.

If TSH values are abnormal at either the one month or two month time points, follow-up will be required at 6 and 12 months after the administration of ISOVUE to monitor subject's response and treatment (if any). Follow-up at the 6 and 12 month post-dose time points will be performed using a pre-defined questionnaire. Each follow-up will take no longer than 20 minutes.

Study Population

The study will be conducted in pediatric subjects 0 to 3 years of age, who are scheduled to undergo a radiologic procedure with intravascular administration of ISOVUE as part of their routine standard of care.

It is planned to enroll approximately 1,560 subjects in order to obtain 1,482 evaluable subjects.

Inclusion Criteria

Enroll a subject in this study if the subject meets the following inclusion criteria:

1. Is male or female from 0 to 3 years of age;
2. Is scheduled to undergo a radiologic examination that requires intravascular administration of ISOVUE as part of his/her standard of care;
3. Has normal baseline thyroid function tests (TSH, total T3, total T4, and fT4) performed at a local laboratory with blood sample obtained within one week prior to ISOVUE administration;
4. Written informed consent is obtained from the subject's parent(s) or legally acceptable representative(s) (according to local regulations) who are willing to comply with the protocol requirements.

Exclusion Criteria

Exclude a subject from this study if the subject does not fulfill the inclusion criteria, or if any of the following conditions are observed:

1. Has any known allergy to one or more of the ingredients of ISOVUE;

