The primary endpoint of this study is to evaluate the proportion of subjects, 0 to 3 years of age, with abnormal TSH values at either one month or two months after administration of ISOVUE. Following FDA recommendations, abnormal TSH in the study is defined as any TSH value above the normal age/gender-specific reference range provided by the respective local laboratories.

Abnormal TSH findings for subjects enrolled in the study will be compared to a reference population. As recommended by the FDA, the reference population for the study is represented by 3,214 infants who received potassium iodide prophylaxis on the second day of life at the time of the Chernobyl nuclear accident; 12 of the 3,214 infants ($p=0.003734$, 95% CI 0.002025, 0.006339) showed a transient increase of serum TSH levels and a decrease of fT4 levels after administration of potassium iodide.¹

The study hypothesis will be:

$$H_0: p \geq 0.003734$$

$$H_A: p < 0.003734$$

The proportion of subjects with abnormal TSH at either one month or two months after administration of ISOVUE and its 95% confidence interval will be estimated. Confidence interval will be calculated based on the approximate normal distribution:

$$95\% \text{ CI} = p \pm 1.96 * (p * (1-p) / n)^{1/2}$$

The number of subjects with shift in serum TSH (with respect to normal reference range) after exposure to ISOVUE will be cross tabulated and summarized separately. Each subject will serve as his/her own control, with the pre-dose values representing their baseline or control values.

Secondary Endpoint - Analysis for Hypothyroidism

The secondary endpoint is to evaluate the proportion of subjects, 0 to 3 years of age, with hypothyroidism regardless of the need for thyroid hormone therapy at either one month or two months after administration of ISOVUE.

Hypothyroidism is defined as a TSH $> 10 \text{ mIU/L}$ (independent of fT4) or as a TSH above the normal age/gender-specific reference range and a fT4 below the lower limit of the normal range.

The proportion of subjects with hypothyroidism at either one month or two months after administration of ISOVUE will be estimated and the 95% confidence interval will be presented.

For those subjects with hypothyroidism, follow-up data will be summarized by monitoring time points (6 months and 12 months).

Secondary Endpoint - Analysis for Thyroid Hormone Replacement Therapy

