The proportion of subjects initiated on thyroid hormone replacement therapy will be estimated with 95% confidence interval.

Analysis for Other Safety Issues

Serious adverse events and non-serious adverse drug reactions will be summarized and listed.

Sample Size

The threshold incidence rate ($p=0.003734$) obtained from the Nauman and Wolff publication¹ will be used as the clinically meaningful value to rule out a safety concern about the proportion of children with abnormal TSH after exposure to ISOVUE. Using confidence interval method for the probability of observing a rare event, when no case is observed out of n , the upper 95% confidence limit of the incidence rate can be estimated by $3/n$. If no cases were observed in the sample size of 1,482, there is 95% confident to rule out an incidence rate of 0.002025 or higher. Considering a 5% drop out rate, 1,560 subjects will be enrolled in the study.

Interim Analyses

No interim analysis is planned.

References

¹ Nauman J, Wolff J. Iodide prophylaxis in Poland after the Chernobyl reactor accident: benefits and risks. Am J Med. 1993 May;94(5):524-32.

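### The planned 1,482 evaluable subjects come from 0.002025, the lower confidence limit of the reference rate, not from the 0.003734 that the protocol says it used and tests

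*Protocol*

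**What the plan says.** Discussion of Study Design states that "sample size estimation for the current study has utilized the threshold incidence rate", giving its value as 0.003734. The Sample Size section opens with the same rate, which "will be used as the clinically meaningful value to rule out a safety concern". The Primary Endpoint section tests it: "H_0: p \geq 0.003734", against the alternative that p is smaller.

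The calculation under Sample Size then takes the upper 95% limit with zero cases as 3/n and concludes that with no cases in 1,482 subjects "there is 95% confident to rule out an incidence rate of 0.002025 or higher". A 5% dropout allowance brings enrolment to 1,560. Study Population repeats both numbers: "It is planned to enroll approximately 1,560 subjects in order to obtain 1,482 evaluable subjects".

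Outside the Sample Size section, 0.002025 appears only as the lower end of the interval around the reference rate of 12 in 3,214 infants: "95% CI 0.002025, 0.006339". The protocol does not say why that limit should set the size.

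For the analysis, the Primary Endpoint section prescribes a two-sided 95% interval from the normal approximation, p ± 1.96 standard errors (the Wald interval).

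**The concern.** Two statements about one calculation cannot both be true. If the size was built on 0.003734, the 3/n rule does not give 1,482. If it was built on 0.002025, the statement under Discussion of Study Design is wrong. The gap is large: the declared threshold would need little more than half the planned subjects.

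Two things are at stake. First, the study takes three blood samples from each of about 1,560 children aged 0 to 3, and the protocol should give the true reason for that number. Second, the Sample Size section speaks of ruling out two different rates in one paragraph. If a few cases occur, the data may exclude one rate and not the other, and the protocol does not say plainly which statement the study is meant to support.

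**Working it through.** **Inputs, all from the protocol.** Declared and tested threshold 0.003734; reference rate 12/3,214 with 95% limits 0.002025 and 0.006339; sizing rule: upper limit = 3/n with zero cases; dropout 5%; planned n 1,482 evaluable and 1,560 enrolled; analysis interval p ± 1.96·√(p(1−p)/n).

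**Step 1: reproduce the planned size.** Solving 3/n = rate for n:

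| Rate in the 3/n rule | n | Evaluable | Enrolled (n/0.95) |
|---|---|---|---|
| 0.002025 | 3/0.002025 = 1,481.5 | 1,482 | 1,482/0.95 = 1,560 |
| 0.003734 | 3/0.003734 = 803.4 | 804 | 804/0.95 = 846.3, so 847 |

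The first row matches the protocol exactly. The second differs by 1,482 − 804 = 678 evaluable and 1,560 − 847 = 713 enrolled. Replacing 3/n by the exact zero-case calculation, ln(0.05)/ln(1 − rate), gives 1,478 and 801, so the approximation does not explain the gap.

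**Step 2: confirm what 0.002025 is.** A mid-P 95% interval for 12/3,214 is 0.002025 to 0.006339, the limits that the protocol prints. So 0.002025 is the lower limit of the reference estimate.

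**Step 3: upper limits at n = 1,482.** The exact limit p_U solves P(X ≤ x | n, p_U) = α, with α = 0.05 (one-sided 95%) or 0.025 (two-sided 95%). Wald for one case: 1/1,482 = 0.000675, standard error 0.000675, upper limit 0.000675 + 1.96 × 0.000675 ≈ 0.001997. Wald for two cases: 0.001350 + 1.96 × 0.000954 ≈ 0.003219.

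| Cases | Exact one-sided 95% | Planned Wald (two-sided 95%) | Exact two-sided 95% |
|---|---|---|---|
| 0 | 0.002019 | 0 (interval collapses) | 0.002486 |
| 1 | 0.003197 | 0.001997 | 0.003754 |
| 2 | 0.004242 | 0.003219 | 0.004866 |
| 3 | 0.005224 | 0.004313 | 0.005904 |

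A result separates the two rates when its upper limit lies between 0.002025 and 0.003734. That happens at one case for the exact one-sided limit, which is the limit that 3/n approximates. It happens at two cases for the planned Wald interval, under which one case falls below both rates. Under the exact two-sided limit, one case fails both rates and zero cases separates them.

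**Step 4: error rate and chance of passing at 0.003734.** If the true rate is 0.003734, the chance of at most 1 case in 1,482 is 0.026 and of at most 2 cases is 0.086. The protocol assumes no true rate, so two are shown as assumptions:

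| Assumed true rate | No case | At most 1 | At most 2 |
|---|---|---|---|
| 0.0005 | 0.48 | 0.83 | 0.96 |
| 0.001 | 0.23 | 0.56 | 0.81 |

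Under the exact one-sided limit, the contrast between ruling out 0.003734 and ruling out 0.002025 is at most 1 case against none. Under Wald it is at most 2 against at most 1.

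**The case against.** The best defence is that nothing was miscalculated and the discrepancy is on the safe side. 3/1,482 = 0.002024 and 1,482/0.95 = 1,560 are correct, and a result that excludes 0.002025 necessarily excludes 0.003734. This stands: the fault is in the stated basis, not in the division, and the study is larger than the declared threshold needs with zero cases. A reader might infer that it is too small, or that 1,560 should be cut to 847. Neither follows. The 804 suffices only if no case occurs, which has a chance of 0.999^804 ≈ 0.45 at an assumed true rate of 0.001.

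A reader might also infer that the protocol has two competing success criteria. It does not. Only 0.003734 is called a threshold and there is one pair of hypotheses; 0.002025 stands in a conditional sentence about zero cases, with no decision attached. What remains is that the sizing sentence speaks of ruling out a rate other than the tested one, without explanation.

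A third tempting reading is that a single case always passes one rate and fails the other. That depends on the interval. It is true for the exact one-sided 95% limit, but not for the planned Wald interval (one case passes both) or the exact two-sided limit (one case fails both).

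A statistical analysis plan, if there is one, may add detail on the interval. It would not correct the protocol's own account of how its sample size was obtained.

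**Conclusion.** The point holds at moderate severity. The planned 1,482 and 1,560 follow from 0.002025, and the statement that 0.003734 was used is wrong as written; by the same rule that rate gives 804 and 847. The tested hypothesis is unaffected and the size is conservative for it.

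The practical consequence is limited to results in a narrow band: one case under the exact one-sided 95% limit (0.00320), or two under the planned Wald interval (0.00322), would exclude 0.003734 but not 0.002025. These counts assume exactly 1,482 evaluable subjects. The finding about the basis of the size needs only the protocol's own figures and its 3/n rule.

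**What to change.** 1. Keep 1,482 evaluable and 1,560 enrolled.
2. In Discussion of Study Design and Sample Size, state that the number was set so that zero cases gives an upper 95% limit at 0.002025, the lower limit of the reference rate, and give the reason. Call this a precision statement, and note that 0.003734 alone would need 804 by the same rule.
3. In Primary Endpoint, state that 0.003734 is the sole decision threshold.
4. Name one interval for the decision and use it in both the sizing and the Primary Endpoint section. The exact one-sided 95% limit matches 3/n. If it replaces Wald for the decision, the largest passing count is 1 case in 1,482, with a type I error of 0.026 at 0.003734.
5. Do not write in that count while the Wald formula remains the decision interval: Wald also passes 2 cases (type I error 0.086), and the protocol would then hold two maximum counts for one hypothesis. If an exact two-sided 95% limit is preferred, the largest passing count is 0 and 3/n no longer matches it.

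The cost is revised text in three sections. Item 4 is a change of analysis method and should be documented as one. No added subjects, visits or data are needed.
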